**Table 4-1 Pharmacokinetic Summary – Part A of OBI-999-001**

		MMAE				OBI-999				
Cohort	Dose (mg/kg)	T max (d)	C max (ng/mL)	AUC (ng*d/mL)	T 1/2 (d)	C max ( $\mu$ g/mL)	AUC ( $\mu$ g*d/mL)	Cl (L/day)	T 1/2 (d)	Vd (L)
1	0.4	0.79	2.7	12.5	2.66	5.9	6	5.3	1.8	8.2
2	0.8	0.38	3.9	16.5	3.51	11.3	15.8	4.2	3.9	8
3	1.2*	0.59	3.9	16.6	2.96	20.6	29.9	2.8	3.6	6.8
4	1.6	2.79	7.6	53.6	3.09	33.7	60.4	2.6	2	5.7

\*data calculated from 5 subjects dosing at 1.2 mg/kg.

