#### **14.4 Pharmacokinetic Analysis**

Pharmacokinetic parameters will be calculated using a non-compartmental method from the PK samples collected during Cycles 1 and 2 and will include, but is not limited to  $C_{max}$ , AUC,  $t_{1/2}$ , Cl,  $T_{max}$ , and  $V_d$ .

To describe the dependency on dose, scatter plots of  $C_{max}$  and AUC versus dose will be provided. Summary statistics will be tabulated for the trough concentration ( $C_{min}$ ) and peak concentrations (end of infusion) by dose and study day.

Pharmacometric methods may also be applied to further investigate OBI-999 and MMAE exposure (e.g., accumulation of OBI-999, presence of dose- or time-dependent OBI-999 PK behavior, verification of influential factors on OBI-999 PK).

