11. DEVIATIONS FROM ANALYSIS AS DESCRIBED IN THE PROTOCOL

In the section §14.2 of the protocol the safety population is defined as all enrolled patients who receive at least 1 dose of study drug. The population used for analysis of clinical activity is defined as all enrolled patients who received at least one dose of study drug and had at least one follow-up tumor assessment scan, but it was not clearly stated this is the efficacy population. We clearly defined it in section §8 of the SAP.

The DOR is defined in section 14.3 of the protocol as the time from date of confirmed PR or CR to date of progression, but as we are applying a censoring rule to patients who are alive at the time of the analysis, we updated the definition in section 9.7.1 of the SAP to time from date of confirmed PR or CR to date of progression or death (from any cause).

OBI-999 2.0 mg/kg was planned to be administered in Part A but this dose was not administered to any subjects in Part A due to the toxicity observed with the 1.6 mg/kg dose. For this reason, this cohort will not be presented.

Efficacy endpoints will be analyzed in the safety and efficacy populations, because the definition of the efficacy population specifies that patients must have at least one follow-up assessment scan and so is closer to a per protocol population.

DLTs will not be derived and will be presented as collected on the eCRF. The following DLTs have been updated:

- “≥ Grade 3 fatigue, nausea and vomiting or diarrhea that does not resolve to Grade 1 or Baseline within 72 hours despite optimal supportive care” has been revised to “≥ Grade 3 fatigue, nausea and vomiting or diarrhea for more than 72 hours despite optimal supportive care”.
- “Any other Grade 3 or Grade 4 non-hematological toxicity (except Grade 3 fatigue, nausea, vomiting, or diarrhea lasting < 24 hours with optimal therapy, Grade 3 non-hematologic laboratory abnormalities that resolve to Grade 1 or baseline within 14 days)” has been

revised to. Any \geq Grade 3 non-hematological toxicity (except Grade 3 fatigue, nausea, vomiting, or diarrhea lasting < 24 hours with optimal therapy, Grade 3 non-hematologic laboratory abnormalities that resolve to Grade 1 or baseline within 14 days)".

On 10 November 2023, Sponsor stated they stop the OBI-999-001 study and elected to generate an aCSR. Therefore, as per sponsor decision, the planned analyses have been changed to:

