20%, the individual AUC_{∞} result and the parameters depending on AUC_{∞} will be listed but flagged as not reliably calculated. They will generally not be included in descriptive statistics and statistical testing procedures.

$AUMC_{\text{last}}$ ($\text{h}^2 \mu\text{g}/\text{mL}$): Area under the first moment of the concentration time curve from time zero to time the last quantifiable time, calculated by log-linear trapezoidal rule.

$AUMC_{\infty}$ ($\text{h}^2 \mu\text{g}/\text{mL}$): Area under the first moment of the concentration-time curve from time zero to infinite time

CL (mL/h): Total body clearance following iv administration

$$- CL = \frac{\text{Total Dose Administered in } \mu\text{g}}{AUC_{\infty}}$$

V_z (mL): Volume of distribution following iv administration

$$- V_z = CL/\lambda$$

V_{ss} (mL): Volume of distribution at steady-state following iv administration

$$- V_{\text{ss}} = \frac{\text{Total Dose Administered in } \mu\text{g} \times AUMC}{(AUC_{\infty})^2}$$

Dose proportionality

- To investigate the dose proportionality of AUC and C_{max} , a statistical analysis using the power model will be conducted. The power model will have the form:
- $Y = a \cdot (\text{dose})^b$, where Y is the PK parameter, and a and b are the coefficient and exponent, respectively, of the power equation.
- By taking the natural logarithm (\ln), the power model can be analyzed using linear regression and has the form:
- $\ln(Y) = \ln(a) + b \cdot \ln(\text{dose}) + \text{error} = \alpha + \beta \cdot \ln(\text{dose}) + \text{error}$,
- where α is the intercept, and β is the slope, and $\ln(\text{dose})$ is based on the dose size for each subject.
- Estimates of slope and intercept along with their 90% confidence intervals will be reported. A minimum of 3 values per dose must be available for a given parameter to estimate dose proportionality using the power model.

All calculations will use the actual post-dose times recorded on the CRF. All computed PK parameters will be listed by subject and summarized by doses group in the Escalation Phase and by disease cohort in the Expansion Phase (mean, standard deviation,

coefficient of variation, minimum, maximum, number of observations). Individual and mean (by time) concentrations versus time will be plotted for each dose on both linear and natural logarithm scales.

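### The PK plan sums up dose proportionality in one power-model slope with no check of the straight-line form, and Table 4-1 suggests that form fails for MMAE

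*SAP*

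**What the plan says.** SAP Appendix III, section 3.4, under its dose proportionality item, says that for AUC and Cmax "a statistical analysis using the power model will be conducted". The model is ln(Y) = α + β·ln(dose) + error, with dose taken as each subject's own dose size. The stated output is "Estimates of slope and intercept along with their 90% confidence intervals will be reported". The one condition is on numbers: "A minimum of 3 values per dose must be available for a given parameter to estimate dose proportionality using the power model". The text names no analyte, gives no acceptance range for the slope, and has no lack-of-fit test, curvature term or comparison between dose levels.

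Other planned outputs also bear on dose:

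- Protocol 14.4 (also in the synopsis) promises a graph: "To describe the dependency on dose, scatter plots of" Cmax and AUC versus dose. SAP section 11 does not list these plots as dropped, but PK Figures 1 to 12 are all concentration-time plots.
- Section 3.4 summarizes every PK parameter by dose group in the escalation part. The shells for PK Tables 5 to 7 include dose-normalized Cmax and AUC, per mg, without confidence intervals for ratios between doses.
- Protocol 14.4 allows optional pharmacometric work on dose-dependent behavior.

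PK parameters are starred in SAP section 8.2 as part of the abbreviated report, so the analysis is still planned.

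**The concern.** One slope describes dose dependence only if log exposure is straight in log dose. If exposure is level over part of the range and steep over another part, the slope averages the two and describes neither. Table 4-1 suggests this for MMAE, the cytotoxic payload. The misfit is largest at 1.2 mg/kg, the RP2D, and at 1.6 mg/kg. SAP section 11 says the 2.0 mg/kg level was not given "due to the toxicity observed with the 1.6 mg/kg dose". A reader who saw only the reported slope and interval for MMAE AUC would learn little about how exposure changes between those two levels. The plan does not say when the slope should not be relied on.

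**Working it through.** The documents state no slope or precision target for dose proportionality, so there is no planned figure to reproduce.

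**Inputs.** These are the Table 4-1 group values at 0.4, 0.8, 1.2 and 1.6 mg/kg. The first two rows read "1 0.4 0.79 2.7 12.5 2.66 5.9 6 5.3 1.8 8.2" and "2 0.8 0.38 3.9 16.5 3.51 11.3 15.8 4.2 3.9 8". The table gives n only at 1.2 mg/kg ("data calculated from 5 subjects dosing at 1.2 mg/kg") and gives no SDs. Nominal mg/kg is used throughout.

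**Step 1: local slopes.** Local slope = ln(ratio of exposures) / ln(ratio of doses). For MMAE AUC:

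- 0.4 to 0.8: ln(16.5/12.5)/ln 2 = 0.278/0.693 = 0.40
- 0.8 to 1.2: ln(16.6/16.5)/ln 1.5 = 0.006/0.405 = 0.01
- 1.2 to 1.6: ln(53.6/16.6)/ln 1.333 = 1.172/0.288 = 4.07

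A proportional relation would give 1 each time. These values need no assumption about n or SD.

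**Step 2: the single slope.** Least squares of ln(value) on ln(dose), four points, equal weights:

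| Parameter | Values | Local slopes | Single slope |
|---|---|---|---|
| MMAE AUC | 12.5, 16.5, 16.6, 53.6 | 0.40, 0.01, 4.07 | 0.85 |
| MMAE Cmax | 2.7, 3.9, 3.9, 7.6 | 0.53, 0.00, 2.32 | 0.63 |
| OBI-999 AUC | 6, 15.8, 29.9, 60.4 | 1.40, 1.57, 2.44 | 1.62 |
| OBI-999 Cmax | 5.9, 11.3, 20.6, 33.7 | 0.94, 1.48, 1.71 | 1.24 |

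For MMAE AUC, Sxy/Sxx = 0.920/1.084 = 0.848. Weighting by assumed cohort sizes in dose order gives 0.85 (3/3/5/4), 0.94 (3/3/6/6) and 0.88 (3/3/10/6). With only 3 subjects at 1.6 mg/kg it falls to 0.78 (3/3/5/3) or 0.67 (3/6/10/3).

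**Step 3: misfit for MMAE AUC.** The predicted 1.6/1.2 ratio is 1.333^β, which is 1.28 at β = 0.85 and 1.31 at β = 0.94. The table shows 53.6/16.6 = 3.23. With equal weights the fitted values are 10.6, 19.0, 26.8 and 34.2. The line is therefore 61% too high at 1.2 mg/kg (26.8/16.6) and 36% too low at 1.6 (34.2/53.6). Over equal weights and the first three sets of cohort sizes, the ranges are 48 to 63% too high and 34 to 41% too low.

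**Step 4: what the interval would show.** Subject values were simulated around the Table 4-1 values with lognormal noise, 6000 runs per setting. The SD of ln(AUC) was assumed to be 0.3, 0.5 or 0.7, with cohort sizes 3/3/5/4, 3/3/6/6 and 3/3/10/6. For MMAE AUC:

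- The 90% interval for the slope contains 1 in 91 to 99% of runs (89 to 91% with 3/3/5/3).
- The median interval width is 0.85 to 1.45.
- A lack-of-fit F test at 10% flags the straight line in 48 to 100% of runs.

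The other parameters differ. Over the same settings, the interval lies wholly above 1 in 48 to 99% of runs for OBI-999 AUC, and wholly below 1 in 23 to 64% for MMAE Cmax.

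**Step 5: the other planned outputs.** Dose-normalized MMAE AUC is 12.5/0.4 = 31.3, 16.5/0.8 = 20.6, 16.6/1.2 = 13.8 and 53.6/1.6 = 33.5 per mg/kg. A dose-normalized summary by dose group would show the fall and the jump.

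**The case against.** A reader might infer that the planned report would declare exposure proportional and conceal the rise at 1.6 mg/kg. The documents do not support that, for three reasons.

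- The reading could arise for MMAE AUC only. OBI-999 AUC would read as more than proportional, and MMAE Cmax points below 1.
- The plan has no criterion for declaring proportionality, and an interval about one unit wide that contains 1 is inconclusive.
- The slope is not the only output on dose. The scatter plots and dose-normalized summaries would make the pattern visible, and Table 4-1 already prints it. Absence from the figure list is weak evidence that the plots were abandoned, since the power model itself has no table shell either.

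The data are also thin. Table 4-1 does not say which kind of average or which AUC it shows, and one unusual subject at 1.6 mg/kg could produce the jump. SAP section 5.1.1 gives 22 patients finally enrolled in Part A, so the final values may differ. The consequence is limited too: the safety review committee has already set the RP2D, and no decision in the documents uses the slope.

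All of this stands, and it narrows the point. What remains is that section 3.4 names one model for dose proportionality, never tests its form, and does not connect it to the outputs that would show the misfit.

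**Conclusion.** The point holds as a minor one. For MMAE the single slope is a poor summary of the group values available: a predicted step of x1.28 to 1.31 against x3.23 for AUC, and a slope of 0.63 against a last-step local slope of 2.32 for Cmax. The likely MMAE AUC result is an inconclusive interval around a slope a little below 1, which the plan leaves open to being read as proportional.

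The ratios and local slopes come straight from Table 4-1. The weighted slopes rest on assumed cohort sizes, and the simulation percentages on those and on assumed SDs. All use nominal mg/kg, whereas the plan uses each subject's own dose. Four group values without SDs suggest non-linearity in MMAE; they do not establish it, and they say nothing about the cause of the toxicity at 1.6 mg/kg.

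**What to change.** In SAP Appendix III, section 3.4, name the analytes and, for each one:

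1. Test lack of fit by comparing the power model with a model holding ln(dose) plus dose level as a factor. Keeping ln(dose) in the larger model matters because the plan uses individual doses and its tables normalize per mg. In mg, ln(dose) varies within a level, so the straight line is not nested in a dose-level factor alone. The comparison is valid for mg or mg/kg. State that power is limited: in the simulations a 5% test flagged MMAE Cmax in only 12 to 79% of runs (SD or CV 0.3 to 0.7; cohorts 3/3/5/3, 3/3/6/6 and 3/3/10/6).
2. Report adjacent-level ratios of dose-normalized geometric mean AUC and Cmax with 90% confidence intervals.
3. Add the protocol's scatter plots of Cmax and AUC versus dose to the PK figure list.
4. State that when lack of fit is flagged, the single slope is not used as the dose-proportionality conclusion and the adjacent-level ratios are reported instead.

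The cost is a short text change, one small table per report and the plots the protocol already promises. No new data are needed. The adjacent-level intervals will be wide at these cohort sizes, and the report should say so.

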**Table 9-3 Part B - Pharmacokinetic and ADA Sampling Schedule**

Cycle	Cycle 1 and Cycle 2					Cycle 3, Cycle 4, Cycle 8, and Every 4 Cycles Thereafter	EoS / ET
	D1	D2	D4	D8	D15		
Cycle Day						D1	$\pm 7$ days
Pharmacokinetic Samples							
Before infusion	X a					X b	
30 minutes after end of infusion (90 min) c	X	X d,g	X d,g	X d	X d	X	X
6 hours after end of infusion (420 min) c,e	X						
Immunogenicity Studies (ADA)f	X					X	X

Abbreviations: ADA = anti-drug antibody; C = Cycle; D = Day; EoS = End of Study; ET = Early Termination; min = minute

OBI-999 infusion should be administered on Day 1 of every 21-day cycle throughout the study treatment period.

The infusion duration of Cycle 1 and Cycle 2 are  $60 \pm 10$  minutes, and can be reduced to  $30 \pm 10$  minutes from Cycle 3, if there were no infusion related adverse events on prior infusions and at the discretion of the Investigator.

- Cycle 1 Day 1 (C1D1) pre-infusion serum samples can be drawn within 1 day prior-to the infusion.
- Pre-infusion serum samples can be collected at any time prior to the infusion on the day of the infusion.
- Post-infusion samples on D1 can be collected in a window of  $\pm 15$  minutes.
- Samples on Days 2, 4, 8, and 15 can be collected in a window of  $\pm 2$  hours based on the end of infusion on Day 1.
- If there is change of the infusion rate or interruption of infusion, the PK sampling on Day 1 are to be collected from the exact time of completion of infusion to obtain the post-infusion samples after the end of infusion. Exact time of sample collection and the reason for interruption should be documented in the eCRF.
- ADA samples will be collected along with pre-infusion PK samples. No post-infusion ADA samples will be collected. For subjects with persistent antibodies at end of study, an additional ADA sample will be collected at 4 months after the end of study visit.
- This intensive PK sampling will be collected from first 5 patients in each cohort.

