2.3. PK Sampling Schedule

Blood (serum) samples will be collected at the following time points: C1D1 Pre-infusion (within 1 day prior-to the infusion), post infusion samples at the end of infusion and at 0.5 (± 15 min), 2 (± 15 min), 4 (± 15 min), 8 (± 15 min), 24 (± 2 h, on Day2), 72 (± 2 h, on Day4),

168 (± 2 h, on Day8), 240 (± 2 h, on Day11) and 336 hours (± 2 h, on Day15) after the end of the infusion.

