3. PHARMACOKINETIC ANALYSIS METHODS

3.1. Analysis Population and Handling of Missing Time Points

The PK population will include all enrolled subjects who receive at least 1 dose of study drug

and have sufficient PK samples (a sample at the end of administration and at least 3 samples

during the elimination phase) to include in the PK assessments. Generally, only values above the lower limit of quantification (LLOQ) are used for the estimation of PK parameters. Unless otherwise specified below, missing sampling or concentration values should not be imputed, but left missing in the calculation of derived PK parameters. If the actual sampling time is missing, but a valid concentration value has been measured, the scheduled protocol time may be used for the calculation of derived PK parameters. Collection of serum samples outside of the protocol defined time window for the time point will not result in exclusion of the sample result from NCA. Values below the lower limit of quantification (LLOQ) will be referred to as below the quantification limit (BQL). BQL values that precede the first PK concentration above the LLOQ will be imputed as 0 for linear plots and for all calculations including NCA and summary statistics. All other BQL values will be treated as missing for all analyses.

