3.3. Dosing and Pharmacokinetic Sampling Summary

Subject dose administration times will be presented ([PK Listing 2](#)). Cases that potentially affect the analysis will be discussed. Protocol deviations related to dosing or PK sampling will be listed ([PK Listing 3](#)) and summarized in the PK Report text. Deviations to be included in the PK Report include:

- Blood specimen not collected
- Serum specimen result not obtained
- Specimen temperature excursion
- Required specimen collected out of window
- Any other deviation determined by the PK analyst to be potentially affect PK

Serum concentrations will be listed by subject ([PK Listing 4-6](#)), with nominal and actual time associated with the sample indicated (nominal time is defined as the time in h since the start time of the dose). Both laboratory reported concentration values, and modified concentration values used for analysis (for instance, imputation of 0 for a BQL value at baseline) will be included, as separate columns, in the listing. Serum drug concentrations will also be summarized ([PK Table 2-4](#)) and plotted. [PK Figure 1](#) to [PK Figure 12](#) will plot all individual subject and mean serum PK profiles, as linear and semi-logarithmic plots, respectively. Subject ID for each individual profile in these figures will be shown in a legend.

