3.4. Definition and Estimation of Individual NCA PK Parameters

PK parameters will be estimated through a NCA using version 8.3 or later of Phoenix® WinNonlin®

(Pharsight Corporation, Cary, NC). Actual post-dose time will be used for the estimation of PK parameters instead of nominal time. Individual PK parameter estimates will be listed ([PK Listing 7-9](#)).

Phoenix® WinNonlin® NCA will use the following settings to compute parameters from plasma PK data:

- Linear Up Log Down calculation method
- Uniform weighting
- Intravenous dose
- Plasma Model Type

- Lambda Z Acceptance Criteria

- $R_{sq_adjusted} \geq 0.80$
- $Span \geq 2.0$ half-lives
- Includes ≥ 3 timepoints after T_{max}

T_{max} (hour): Time to reach the maximum concentration

- directly taken from the observed concentration

C_{max} ($\mu\text{g/mL}$): Maximum concentration

- directly taken from the observed concentration

C_{last} ($\mu\text{g/mL}$): Concentration at last quantifiable time point

- directly taken from the observed concentration

λ (1/h): Elimination rate constant associated with the terminal phase

- estimated terminal slope of the linear regression of log-transformed concentration vs time
- The regression analysis should contain data from at least 3 different time points in the terminal phase and as many data points as possible, always including the last quantifiable concentration but excluding the concentration at T_{max} .
- The coefficient of determination Adj_RSq^2 should be larger than or equal to 0.80. If at least one of these three conditions is not fulfilled, the terminal half-life and the parameters depending on $t_{1/2}$ will be listed but flagged as not reliably calculated. They will generally be excluded from descriptive statistics and statistical testing procedures.

$t_{1/2}$ (h): Terminal elimination half-life

$$- t_{1/2} = \frac{\log_e 2}{\lambda}$$

AUC_{last} ($\text{h}^*\mu\text{g/mL}$): Area under the concentration-time curve from time zero to time the last quantifiable time, calculated by log-linear trapezoidal rule.

AUC_{∞} ($\text{h}^*\mu\text{g/mL}$): Area under the concentration-time curve from time zero to infinite time

- The percentage of extrapolated AUC should not exceed 20% of AUC_{∞} for each individual profile. If the percentage of extrapolated AUC is more than

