UXX-003	X	X	X	X	X	X	X	X	X	X
...	X	X	X	X	X	X	X	X	X	X
Statistics										
N₂	X	X	X	X	X	X	X	X	X	X
Mean	X.X	X.X	X.X	X.X	X.X	X.X	X.X	X.X	X.X	X.X
SD	X.X	X.X	X.X	X.X	X.X	X.X	X.X	X.X	X.X	X.X
GM	X.X	X.X	X.X	X.X	X.X	X.X	X.X	X.X	X.X	X.X
(Min, Max)	(x, x)	(x, x)	(x, x)	(x, x)	(x, x)	(x, x)	(x, x)	(x, x)	(x, x)	(x, x)

		x)							
--	--	----	----	----	----	----	----	----	--

¹ Times are relative to time of dosing.² Number of data points used to compute the summary statistics. For calculation of summary statistics, BQL values were imputed as 0 if they did not come after a PK sample concentration that is above the LLOQ and treated as missing otherwise.**PK Table 5: Summary Statistics for PK Parameters of OBI-999**

Statistic	T _{max} (h)	C _{max} (μ g/mL)	C _{max_D} (μ g/mL/mg)	AUC _(0-last) (h \times μ g/mL)	AUC _{(0-last)_D} (h \times μ g/mL/mg)	CL (L/h)	t _{1/2} (h)	V _{ss} (L)
N								
Mean								
SD								
Min								
Median								
Max								
CV %								
GM								
GSD								

PK Table 6: Summary Statistics for PK Parameters of total antibody

Statistic	T _{max} (h)	C _{max} (μ g/mL)	C _{max_D} (μ g/mL/mg)	AUC _(0-last) (h \times μ g/mL)	AUC _{(0-last)_D} (h \times μ g/mL/mg)	CL (L/h)	t _{1/2} (h)	V _{ss} (L)
N								
Mean								
SD								
Min								
Median								
Max								
CV %								
GM								
GSD								

PK Table 7: Summary Statistics for PK Parameters of MMAE

[figure not shown]
Statistic	T _{max} (h)	C _{max} (ng/mL)	C _{max_D} (ng/mL/mg)	AUC _(0-last) (h \times ng/mL)	AUC _{(0-last)_D} (h \times ng/mL/mg)	t _{1/2} (h)
N						
Mean						
SD						
Min						
Median						
Max						
CV %						
GM						
GSD						

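### PK Appendix III lists only Part A sampling times and pools intensively and sparsely sampled Part B patients, so cohort OBI-999 AUC(0-last) reads high whenever sparse profiles enter the analysis

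*SAP*

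**What the plan says.** **Sampling in Part B.** Protocol Table 9-3, repeated in SAP Appendix I, takes pre-dose, 0.5, 6, 168 and 336 h samples from every patient in Cycles 1 and 2. The Day 2 and Day 4 samples (24 and 72 h) carry a footnote: "This intensive PK sampling will be collected from first 5 patients in each cohort".

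**Sampling in Appendix III.** Section 2.3 gives one list, for Cycle 1 only: "post infusion samples at the end of infusion and at 0.5", 2, 4, 8, 24, 72, 168, 240 and 336 h. These are the Part A times plus an end-of-infusion draw that neither protocol sampling table contains. The shells for PK Tables 2 to 4 use the Part A nominal times; Part B's 6 h sample, nominal 7 h from the start of dosing, has no column.

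**Summaries.** Section 3.4 states the grouping: "All computed PK parameters will be listed by subject and summarized by doses group in the Escalation Phase and by disease cohort". For Part B, cohort is thus the only grouping. The shell "PK Table 5: Summary Statistics for PK Parameters of OBI-999" reports AUC(0-last), CL, half-life and Vss, with no row or column for sampling intensity.

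**Who is in.** Section 3.1 admits patients who "have sufficient PK samples (a sample at the end of administration and at least 3 samples" in the elimination phase. That phase is given no start time. In section 3.4 the software setting asks for three time points later than Tmax, whereas the text says: "The regression analysis should contain data from at least 3 different time points in the terminal phase".

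**Reliability rules.** Section 3.4 flags half-life, AUC-infinity and parameters that depend on them. AUC(0-last) has no such rule.

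**The concern.** Linear-up/log-down integration is exact for a single exponential decline. For a curve that falls fast and then slowly, a log-linear chord lies above the curve, and the error grows with the gap between samples. The intensive patients break the stretch from 6 to 168 h at 24 and 72 h; the others cross it in one step. Two patients with the same true exposure would then get different AUC values, and the planned cohort mean would mix them.

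Characterizing PK is a stated aim of Part B (SAP section 5.1.3). A reader comparing cohorts, or Part B with the 1.2 mg/kg group of Part A, could take a sampling artefact for a difference in exposure. The number of patients behind each summary is also not fixed by the text.

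**Working it through.** **Inputs.** Protocol Table 4-1, 1.2 mg/kg row, OBI-999: Cmax 20.6 µg/mL, AUC 29.9 µg·d/mL, CL 2.8 L/day, half-life 3.6 d, Vd 6.8 L. Integration rule from Appendix III section 3.4. LLOQ 15 ng/mL from Appendix III section 2.4.

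**1. Is the decline multiphasic?** For one compartment, AUC ≈ Cmax × t½ / ln 2 = 20.6 × 3.6 / 0.693 = 107, against the stated 29.9, a ratio of 3.6. The same ratio on the 0.4, 0.8 and 1.6 mg/kg rows is 2.6, 4.0 and 1.6. All exceed 1, so a single exponential does not fit the table.

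**2. Assumed curve.** A two-compartment curve with a 1 h infusion, A + B = 20.6, A/α + B/β = 29.9 and β = ln 2 / 3.6 = 0.193/d. Vd is read as a steady-state volume, so mean residence time = 6.8/2.8 = 2.43 d. (A terminal-phase volume would be CL/β = 2.8 × 3.6 / 0.693 = 14.5 L, not 6.8.) Solution: A = 18.71, B = 1.89 µg/mL, α = 0.932/d.

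**3. Consistency check.** On the Part A schedule this curve gives AUC(0-last) = 29.88 against the table's 29.9. Because 29.9 was used in the fit, this checks the coding only.

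**4. The two Part B schedules on the same curve.** Modelled concentrations at nominal 7, 25, 73, 169 and 337 h are 16.33, 8.78, 2.18, 0.517 and 0.127 µg/mL. The last is 127 ng/mL, above the LLOQ.

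Sparse, 7 to 169 h (6.75 d): 6.75 × (16.33 − 0.517) / ln(16.33/0.517) = 30.92. Intensive, same span: 9.12 + 9.47 + 4.62 = 23.21.

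| Interval (nominal h) | Sparse | Intensive |
|---|---|---|
| 0–1.5 | 0.62 | 0.62 |
| 1.5–7 | 4.14 | 4.14 |
| 7–169 | 30.92 | 23.21 |
| 169–337 | 1.95 | 1.95 |
| AUC(0-last), µg·d/mL | 37.62 | 29.92 |

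The true AUC to 337 h is 29.24. Sparse/intensive = 37.62/29.92 = 1.257; sparse is 29% and intensive 2% above true.

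**5. Would the plan's checks catch it?** The noise-free sparse fit (6, 168, 336 h) has adjusted R² 0.88, a span of 7.0 half-lives and 1.0% extrapolation, so it passes all three. Its half-life reads 1.97 d; the intensive fit gives 2.76 d and the curve has 3.6 d. CL sparse/intensive is 0.80.

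**6. Sensitivity.** With the terminal-phase share of AUC varied from 10% to 80%, the sparse excess over intensive runs from 8.6% to 42.1%. With mono-exponential decline it is 0.

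**7. Cohort mean.** With 4 sparse of 9: (4 × 1.257 + 5)/9 = 1.114. Over the range in step 6: (4 × 1.086 + 5)/9 = 1.038 to (4 × 1.421 + 5)/9 = 1.187. With 6 of 11 (a full first stage plus the two pancreatic replacements in SAP section 5.4): (6 × 1.257 + 5)/11 = 1.140.

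**8. Do sparse patients enter?** In Cycle 1 they have 6, 168 and 336 h after the first draw: three if 6 h counts as elimination phase, two if not. But Table 9-3 also gives them pre-dose, 168 h and 336 h samples in Cycle 2, and protocol section 11.2 takes NCA from both cycles. The modelled value at 504 h, the Cycle 2 pre-dose time, is 33 ng/mL, above the LLOQ. A patient who reaches Cycle 2 can therefore have three late samples without the 6 h one. Appendix III does not mention Cycle 2 samples.

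**The case against.** The best defence is that the information is not lost. Appendix I carries the Part B schedule with its first-five note, the subject listings give nominal and actual times and NCA exclusions, and section 3.3 promises: "Cases that potentially affect the analysis will be discussed". Protocol section 14.4 also allows pharmacometric methods, which could handle sparse profiles. That stands as far as it goes: a careful reader could rebuild the split. But the modelling is optional, and none of this commits to a stratified table or defines the elimination phase.

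A second defence is precision. Restricting to five patients costs more than it gains if AUC varies widely between patients: pooling has the lower mean squared error once the between-patient CV exceeds about 0.114/√(1/5 − 1/9) = 38%. This stands, and is a reason to show both groups rather than drop one.

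Stronger readings are tempting but not supported. A reader might infer that, if the 6 h sample does not count, sparse patients drop out, each cohort rests on at most five, and the bias vanishes. Step 8 shows that Cycle 2 samples may admit them, and the 6 to 168 h trapezoid then remains in their Cycle 1 AUC. For the same reason, a five-versus-nine contrast for the ADA denominator in the PK population does not follow; ADA is also reported in the safety population, which PK sampling does not touch. A cohort of 19 with 14 sparse is a design maximum only; SAP section 5.4 says that the study stopped before the formal go/no-go analysis.

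**Conclusion.** The point holds as a minor one. Appendix III omits the Part B schedule and pools two sampling designs whose AUC(0-last) values are not comparable for OBI-999. On the matched 1.2 mg/kg curve a sparse profile reads about 26% above an intensive one (9% to 42% over the curves tried), and a cohort mean about 11% high with 4 sparse of 9.

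The direction rests on multiphasic decline, which Table 4-1 supports. The size rests on group means, a two-compartment form, Vd read as a steady-state volume, and cohort sizes that the documents do not give. The figures apply to OBI-999 only. Total antibody and MMAE were not modelled, and MMAE's Tmax of 0.59 d (about 14 h) falls inside the unsampled gap, so its error could behave differently.

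No decision rule uses these summaries, and the RP2D was already set. The SAP also disagrees with itself on whether they reach the abbreviated report: section 8.2 stars the PK parameters for both parts, section 10.7.2 leaves them unstarred, and section 10.7 limits the report to starred analyses.

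**What to change.** In Appendix III:

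- (a) Add the Part B schedule for Cycles 1 and 2, with the first-five rule, to section 2.3, and a nominal 7 h column to the shells of PK Tables 2 to 4.
- (b) In PK Table 5, show Part B AUC(0-last), CL, half-life and Vss separately for patients with and without Day 2 and Day 4 samples, keeping both groups.
- (c) State which samples count as elimination phase, naming the 6 h and Cycle 2 samples, and say that the 30-minute post-infusion sample serves as the end-of-administration sample.

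Also reconcile the stars in SAP sections 8.2 and 10.7.2.

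The cost is wording and table shells; no new samples or data are needed. Stratified rows rest on fewer patients each, at most five per cohort in the intensive group. Even there half-life reads short on the assumed curve (2.76 d against 3.6 d), so the split removes the difference between schedules and not every limit of the sampling.
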